Study Title: Family Routines – Healthy Families

Protocol version: 29 Aug 2016

IRB number: 2016-154

NCT number: NCT03255902

Principal Investigator: **[name].**

Study Site: William Beaumont Hospital

William Beaumont Children's Hospital
[name]
[name]
U.S.A.

Family Routines – Healthy Families

Specific Aims

Type 1 diabetes is one of the leading chronic diseases of childhood.¹ Families live meal to meal carefully adhering to a complex treatment plan that includes insulin injections, blood glucose monitoring, following a prescribed meal plan, and exercise. The American Diabetes Association (ADA) now recommends that children under 6 years old diagnosed with type 1 diabetes strive to maintain an A1C level lower than 7.5 percent.² Maintaining such tight glycemic control requires that parents carefully monitor blood glucose and eating behaviors so that they can accurately calculate insulin dosing. However, home life for families of young children can be unstructured, thus creating logistic problems related to glycemic control, especially during the evening hours. For example, if there is less than 2 hours between dinner and a bedtime snack, the bedtime blood glucose reading may be above the targeted range and parents are unsure of how to handle the blood glucose result. This can result in overnight hyperglycemia, and an elevated A1C. In addition, mothers report feelings of intense “constant vigilance” due to fear of hypoglycemia and this constant watchfulness has a negative effect on quality of life for parents.³

Even though parents of children with type 1 diabetes report that they (parents) are confident in their diabetes specific skills, e.g., blood glucose monitoring and insulin injection, within one year after diagnosis, in fact, diabetes specific self-efficacy has not been found to be correlated to child metabolic control.⁴ Because the consequences of hypoglycemia are dangerous, parents often err on the side of under-dosing with insulin to avoid these consequences. We propose that a structured evening routine would (a) reduce snacking after dinner and (b) ensure at least two hours between dinner and bedtime glucose readings which in turn would help parents in their decision making process at bedtime.

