Aim 1. Examine the feasibility of a six session parenting skills and family evening routine intervention delivered in a group format. Post intervention interviews and attendance will determine suitability/preferences for mode of delivery and realism of behavioral expectations.

Aim 2. To develop preliminary evidence regarding the impact of a six-session family intervention on child evening routine and glucose control as measured by four indicators:

- a) time between dinner and bedtime glucose readings
- b) difference between bedtime blood glucose reading and morning fasting blood glucose reading
- c) parent decision making and response to bedtime snack/insulin questionnaire
- d) difference between child A1C pre- and 3 months post- intervention through chart review

Aim 3. Determine impact of Family Routines – Healthy Families intervention on parental quality of life for parents of young children with type 1 diabetes.

[figure not shown]
Background and Significance: Type 1 diabetes: Type 1 diabetes is one of the leading chronic diseases of childhood, affecting approximately 167,000 youth under the age of 20 years in the United States.¹ The incidence of type 1 diabetes is rising worldwide, particularly in young children under five years of age.^{10,11} It has been projected that the number of youth in the United States with type 1 diabetes could nearly triple by mid-century.¹² While much work is being done in immunology for the prevention of type 1 diabetes and in technology for a closed-loop artificial pancreas, the reality is that many families must still live meal to meal with the complex work of managing the disease. Recently, the American Diabetes Association (ADA) lowered its target recommendation for blood glucose levels for children with type 1 diabetes. The ADA now recommends that **all** children under the age of 19 diagnosed with type 1 diabetes strive to maintain an A1C level lower than 7.5 percent.² An A1C level of 7.5% corresponds to a three month average blood glucose concentration of approximately 170 mg/dl. This target concentration was lowered due to growing evidence of the potential risks of hyperglycemia and glucose variability on short term neurocognitive function. In addition, the ADA wanted to bring their recommendation in to alignment with those of the International Society for Pediatric and Adolescent Diabetes.

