Design: This feasibility study will be a mixed methods non-randomized trial to examine the feasibility of combining a parent skill training intervention with a family evening routine intervention. Evidence of feasibility will include attendance, activities completed, and interviews. Families will be recruited from a suburban not-for-profit medical center. Initial set of patients to contact will be provided by data manager for all families who meet inclusion criteria. Patient list will be prioritized by Principal investigator and co-investigators. Study team will verify HbA1c meets criteria, then will call families to see if they are interested in study. If family is interested the consent will be sent to their home and then recalled to see if they want to be scheduled for the classes. If yes, they will be scheduled. Scheduling will stop once we have 12 families who wish to participate. Actual signed consents and interventions will happen at the first session.

Sample:

The sample will include 12 primary caregivers whose children have type 1 diabetes. Inclusion criteria will be (1) self-identification as primary caregiver (2) child aged 2-5 years (3) Child is newly diagnosed or Child's most recent HbA1c is ≥ 8.0 ; and (4) English fluency.

Intervention (See Table 1):

The Incredible Years parenting program is a well-established evidence based program that has been shown in randomized trials to promote positive parenting skills and reduce child behavior problems.²⁴ The program has proven effective in community settings with diverse populations.^{23,25,26} This curriculum targets the specific areas noted above: anger management, communication skills and positive parenting skills.

Family Routines-Healthy Families is a six week program that will assist parents in establishing consistent routines during the evening hours. This includes having dinner about the same time most nights, completing a transition to bedtime routine that should occur in the two hours after dinner and

before bedtime glucose check, and that may include activities such as bath time, story time, and brushing teeth.

Variables and Measures:

Demographics: Standard demographic items will be used to assess age of child, age of caregiver, socioeconomic status, employment status, marital status, level of education and race.

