Aim 2.a. Determine the degree to which a six-session parenting/family routine intervention will positively affect child evening routine. We will perform a paired t-test using the glucometer data for the times of dinner glucose reading and the bedtime glucose reading. Data will be gathered weekly at each educational session for analysis.

Aim 2.b. Determine the degree to which a six-session parenting/family routine intervention will affect the overnight glucose control of preschool age children with type 1 diabetes during the intervention. We will use descriptive statistics to describe the mean difference and absolute difference between the bedtime

glucose reading and fasting morning glucose reading. Data will be gathered weekly at each educational session for analysis.

Aim 2.c. Determine the degree to which a six-session parenting/family routine intervention impacts parental decision making at bedtime based on degree of change between pre and post response to bedtime snack/insulin questionnaire. We will use paired t-tests using the before and after scores on the questionnaire.

Aim 2.d. Determine change in child A1C pre and 3 month post intervention. Descriptive statistics will be used to describe the mean difference and absolute difference in A1C.

Aim 3. Compare PROMIS Psychosocial Illness Impact scores pre and post intervention.

Statement related to parental (self) management and complexity:

The new ADA guidelines for lower A1C in preschool age children makes it imperative that the health care community find ways to assist families of young children in their management of type 1 diabetes. Treatment regimens for tight glucose control in very young children can be very complex for their parents and caregivers. Parent management of diabetes is self-management in this young age group. This proposed study will examine the feasibility of delivering an intervention that includes positive parenting skills and establishment of evening routine that may improve overnight glucose control. This in turn may improve metabolic control. Preliminary data will be used to respond to a NIH/NIDDK FOA for improving diabetes management in children with type 1 diabetes (DP3), specifically to test the intervention in a larger trial and convert to a web-based approach that would be available to families in rural and underserved areas.

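### Aim 2.b reads the bedtime-to-morning glucose difference as overnight control, but the programme is designed to change when the bedtime reading is taken, so the difference may shift with no overnight change

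*Combined protocol and SAP*

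**What the plan says.** The opening Specific Aims section proposes that "a structured evening routine would (a) reduce snacking after dinner and (b) ensure at least two hours between dinner and bedtime glucose readings". Methods, Intervention builds this into the programme: families work on "completing a transition to bedtime routine that should occur in the two hours after dinner and" before the bedtime check. The same opening section explains why the gap matters: "if there is less than 2 hours between dinner and a bedtime snack, the bedtime blood glucose reading may be above the targeted range".

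The list of aims gives indicator (b) as the "difference between bedtime blood glucose reading and morning fasting blood glucose reading". In the Data Analysis Plan:

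- Aim 2.a analyses the interval itself: "We will perform a paired t-test using the glucometer data for the times of dinner glucose reading and the bedtime glucose reading".
- Aim 2.b asks how far the programme will "affect the overnight glucose control of preschool age children with type 1 diabetes during the intervention". Its analysis is descriptive: "We will use descriptive statistics to describe the mean difference and absolute difference between the bedtime" and fasting morning readings, with data collected weekly at the sessions.

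Variables and Measures records the times of the dinner and bedtime readings, and the bedtime and morning glucose values, all verified against the glucometer. No analysis of morning glucose alone is planned, and Aim 2.b makes no allowance for time since dinner. Methods, Design states: "This feasibility study will be a mixed methods non-randomized trial".

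**The concern.** One of the two readings that form the Aim 2.b outcome is taken at a time the programme deliberately moves. If the bedtime value depends on time since eating, as the protocol's rationale implies, a family that lengthens its evening gap can change the bedtime-to-morning difference without any change between bedtime and morning.

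Aim 2.b carries the label of overnight control. A reader who sees the interval lengthen (2.a) and the difference move (2.b) could take these as two findings when the second partly restates the first. With no comparison group, nothing in the design would reveal this. The closing statement on parental management says that the preliminary data will support a funding application for a larger trial, so the reading given to 2.b would carry forward.

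**Working it through.** **Plan's own figure.** There is none to reproduce. Aim 2.b states no expected difference, and the documents give no baseline interval, glucose slope or standard deviation.

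**Structure.** Let B(t) be glucose t minutes after dinner, M the fasting morning value, and D = B(t) − M. Use subscript 0 for an early week and 1 for a late week. Then

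D1 − D0 = [B0(t1) − B0(t0)] + [B1(t1) − B0(t1)] − [M1 − M0].

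- The first bracket is sampling time alone: the same evening curve read at a different minute.
- The second is a real change in evening glucose, for example from less snacking.
- The third is a change in the morning value.

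The plan reports only a summary of D, so the three cannot be told apart. If the evening curve and the morning value are unchanged, the last two brackets vanish and D still moves by the first. The first bracket is zero on any night with t1 = t0, so the average shift over all nights depends on how many nights lengthen.

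**Illustration (every input is an assumption).** Take a post-dinner excursion E(t) = A × (t/tp) × exp(1 − t/tp), with peak A from 40 to 120 mg/dl and time to peak tp from 45 to 75 minutes. Move the reading from 75 to 120 minutes:

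| A (mg/dl) | tp (min) | E(75) | E(120) | Change |
|---|---|---|---|---|
| 40 | 75 | 40.0 | 35.1 | −4.9 |
| 80 | 60 | 77.9 | 58.9 | −19.0 |
| 120 | 45 | 102.7 | 60.4 | −42.2 |

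(Changes are computed before rounding.) These are the smallest, central and largest results over the values tried, so the bedtime value falls by about 5 to 42 mg/dl.

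Other cases:

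- **No change in gap (120 to 120 minutes):** shift 0.
- **Early reading before the peak (30 to 120 minutes, tp = 75):** the bedtime value rises by 6.0 (A = 40) to 17.9 mg/dl (A = 120), so the sign reverses.
- **Straight-line fall instead of a curve:** 10 mg/dl per hour over 30 minutes gives 10 × 30/60 = 5 mg/dl. At 40 mg/dl per hour over 60 minutes it is 40 × 60/60 = 40 mg/dl.

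**Absolute difference.** In the central case with an assumed base of 170 mg/dl, bedtime goes from 170 + 77.9 = 247.9 to 170 + 58.9 = 228.9 mg/dl.

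- Morning 170: the absolute difference goes from 77.9 to 58.9, an apparent improvement.
- Morning 250: it goes from 2.1 to 21.1, an apparent worsening.

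The evening curve and the morning value are the same before and after in both cases. Only the minute of sampling has changed.

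**The case against.** The best defence is that a lower bedtime reading is partly what the programme is for. Specific Aims names the bedtime reading and overnight control as two targets, and less snacking or different bedtime decisions can change glucose itself. That stands: an observed change in the difference need not be an artefact. But because the protocol names two targets, a summary that merges them should not carry the label of only one.

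It is also fair to say that Aim 2.b is descriptive, has no test or success criterion, sits in a 12-family feasibility study, and defines no pre-intervention glucose period. A formal before-and-after contrast is therefore not planned. This limits the harm without removing it, since weekly data cover the very period in which the gap is meant to lengthen. A1C (Aim 2.d) does not depend on bedtime sampling time, but it does not repair 2.b.

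Three stronger readings are tempting, and the documents do not support them.

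- **Success on 2.a must by itself produce an effect on 2.b.** No baseline gap is given, families already at two hours show no timing shift, and the direction can vary.
- **The protocol says an early reading is still on the post-meal rise.** It says only that the reading may be above range, in a sentence about the gap between dinner and a bedtime snack. A sample that was still rising would tend to be higher later, not lower.
- **Early and late weeks can be compared like for like within two-hour nights.** The programme changes which nights and families reach two hours, and a night at exactly two hours qualifies along with much longer gaps.

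**Conclusion.** The concern holds in a conditional form. The bedtime-to-morning difference may shift across programme weeks on nights whose dinner-to-bedtime gap lengthens, without any overnight change, and the plan as written would describe that shift under overnight control. This follows from the protocol's own account of the intervention and from the definition of the outcome.

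The size cannot be taken from the documents. The working range of 5 to 42 mg/dl for a 75-to-120-minute move rests on assumed curves and assumed starting times, and zero and reversed shifts are also possible. It would be wrong to infer that any observed change in 2.b is spurious. The supported conclusion is that timing, evening glucose and morning glucose are mixed in one figure. The point affects the interpretation of one descriptive indicator and leaves the feasibility aim untouched, but it is cheap to correct.

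**What to change.** Amend the Aim 2.b analysis text as follows.

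1. Report fasting morning glucose and bedtime glucose separately by week, alongside their mean and absolute difference.
2. Present the difference by recorded dinner-to-bedtime interval, either under two hours versus two hours or more, or adjusted for minutes within child. Note that the recorded clock starts at the dinner glucose reading, not at the end of eating.
3. State that the all-nights difference also reflects sampling time.
4. Describe a lower bedtime value as a bedtime finding, not an overnight one.
5. If early and late weeks are compared among two-hour nights only, do so within child and label the comparison exploratory, because the programme changes which nights and families qualify.

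All inputs are already collected under Variables and Measures. The cost is a little more descriptive analysis and few nights in some strata, especially two-hour nights in the early weeks. Stratifying or adjusting will not isolate the effect of snacking, since Variables and Measures does not list snack times after dinner.

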Researchers are now investigating the protective mechanisms of family routines and their influence on childhood chronic illness management such as asthma and type 1 diabetes.^{5,6} Family routines have been defined as the regularity of certain activities engaged in by a family.⁷ Evidence is mounting that family routines mediate behavioral problems and adherence in children with type 1 diabetes.⁶ In addition, authoritative parenting in which parents are able to set consistent, realistic limits on children's behavior in a warm and sensitive manner has been linked to better diabetes-specific regimen adherence and metabolic control in young children.⁸ A family based intervention that incorporates an educational and a behavioral component to improve both parenting skills and child evening routines is likely to improve metabolic control by improving both the bedtime blood glucose reading and the overnight glucose control.

The purpose of the proposed study, Family Routines – Healthy Families, is to examine the feasibility and acceptability of a parenting/family routine intervention program for parents of young children, ages 2-5, with type 1 diabetes. The intervention, Family Routines – Healthy Families, contains an established and effective parent skills training curriculum, *The Incredible Years*,⁹ uniquely integrated with a newly developed family evening routine component e.g., family dinner time and evening routine, to promote improved metabolic control. The evening routine component was developed by [name] based on her more than 20 years of clinical experience in working with these families. The team includes [name] MD, Section Head, Pediatric Endocrinology & Metabolism at Beaumont Children's Hospital and [name] PhD, BCBA-D, Licensed Psychologist and Board Certified Behavior Analyst. [name] is specifically trained to deliver *The Incredible Years* curriculum. We will assess outcomes during and at one week post intervention. Outcome measures will include family routine, specifically the time between the dinner and bedtime glucose check, parent bedtime decision making, and child overnight glucose control. In addition, parental quality of life and receptiveness to the intervention will be assessed.

The **Specific Aims** are:

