Feasibility: Feasibility of this intervention will be examined by documenting (a) attendance and (b) the extent to which caregivers carry out the required activities. In addition, feasibility will be examined by interviewing caregivers at the end of the intervention to obtain their perspectives about a) the intervention; b) their perception of the potential burden and benefits c) whether the intervention impacted their decision making or fear of overnight hypoglycemia, and d) any other information that is missing or needs to be addressed. The semi-structured interviews will last about 30 minutes, be audio-recorded, and transcribed verbatim. An Interview Guide will be used to ask open-ended questions about the measures' content and format, and to ask for any additional information participants may wish to share about their experience.

Child Evening Routine: Families will record time of dinner glucose reading and time of bedtime glucose reading. The time of the glucose readings will be verified with the information stored in the glucometer.

Child Overnight Glucose Control: Each child's bedtime and fasting morning blood glucose control will be documented and verified with information stored in the glucometer.

Parental Decision-making: A short survey will be given both pre and post intervention to determine parent perception of decision making at bedtime. See Attachment 1

Psychosocial Illness Impact: Parental quality of life will be measured with both positive and negative items from the PROMIS Psychosocial Impact item bank.

Child Metabolic Control: Most recent A1C will be retrieved from child's medical record.

Data Analysis Plan

Descriptive statistics and paired t-tests will be used to analyze the data. In addition qualitative methods will be used for Aim 1.

Aim 1. Examine the feasibility of a six session parenting/family routine intervention delivered at a suburban health care system site. Attendance and post intervention interviews will determine realism of behavioral expectations. Qualitative analyses will be performed by the PI using the constant comparative method (Glaser, 1992) to identify common themes, identify potential revisions, and modify instruments and procedures. Content analysis (Boyatzis, 1998) of the data will be performed to determine frequency and type of issues identified. Qualitative software, NVivo, will be used to facilitate management of the qualitative data.

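### Aim 2.b asks how far the programme affects overnight glucose control, but its stated analysis describes a bedtime-to-morning difference with no comparison over time

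*Combined protocol and SAP*

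**What the plan says.** The Specific Aims list four indicators meant to give preliminary evidence of impact on evening routine and glucose control. Indicator b is the "difference between bedtime blood glucose reading and morning fasting blood glucose reading".

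In the Data Analysis Plan, Aim 2.b is to determine the degree to which the intervention "will affect the overnight glucose control of preschool age children with type 1 diabetes during the intervention". The method is given in one sentence: "We will use descriptive statistics to describe the mean difference and absolute difference between the bedtime" value and the fasting one the next morning. The readings are collected at every weekly session.

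The neighbouring aims are worded differently. Indicator d is the "difference between child A1C pre- and 3 months post- intervention through chart review". For Aim 2.c the plan says: "We will use paired t-tests using the before and after scores on the questionnaire". Aim 3 compares PROMIS scores before and after the programme.

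Other relevant statements:
- The Data Analysis Plan opens with a general line: "Descriptive statistics and paired t-tests will be used to analyze the data".
- On timing, the Specific Aims say: "We will assess outcomes during and at one week post intervention".
- Under Design, the study is non-randomized with no comparison group described, and consent and intervention both start at the first session.
- Under Variables and Measures, bedtime and fasting readings are documented and checked against the glucometer's memory. No timing is given for this measure, whereas the decision-making survey is given before and after.

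**The concern.** The word *difference* does two jobs in this plan. In Aim 2.d it is a change from before to after. In Aim 2.b it is the outcome measurement itself: the gap between a bedtime reading and the following fasting reading. Skimmed quickly, Aim 2.b looks like a change score, but no change over time is specified.

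A statement about effect needs at least a contrast between an earlier and a later period in the same child. Without one, the analysis reports how large the overnight gap was among these families. The same figure could come from children whose control improved, stayed the same or worsened.

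Overnight glucose is also the middle link in the study's rationale, from evening routine through overnight control to A1C. The Data Analysis Plan section says the preliminary data will support a funding application for a larger trial. An indicator that shows a level but no change would add little to that case.

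**Working it through.** The plan gives no sample-size calculation, SD, effect size or target precision, so there is no figure to reproduce. The check has three parts.

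**1. The aims side by side** (Specific Aims and Data Analysis Plan)

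| Aim | Quantity analysed | Contrast over time named? |
|---|---|---|
| 2.b | bedtime reading versus fasting morning reading, mean and absolute difference | none |
| 2.c | questionnaire scores, paired t-test | before versus after |
| 2.d | A1C, mean and absolute difference, descriptive | before versus 3 months after |
| 3 | PROMIS Psychosocial Illness Impact scores | before versus after |

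Aim 2.d is the useful comparator. It too is purely descriptive, yet it describes a change. What Aim 2.b lacks is therefore a time contrast, not a hypothesis test. The general line on paired t-tests does not supply it, because Aim 2.b is specifically assigned descriptive statistics. That the two readings belong to the same night is the natural reading, though the plan does not say so literally.

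**2. What a summary without a time contrast can hide (conditional illustration)**

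The plan does not say whether the weekly data are pooled or shown by week. If they were pooled with equal weight, the summary would be the sum of the six weekly means divided by 6. With assumed weekly means in mg/dl:

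- shrinking: (60 + 50 + 40 + 30 + 20 + 10)/6 = 210/6 = 35; week 6 minus week 1 = −50
- flat: (35 × 6)/6 = 35; week 6 minus week 1 = 0
- growing: (10 + 20 + 30 + 40 + 50 + 60)/6 = 210/6 = 35; week 6 minus week 1 = +50

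Three opposite courses give one pooled mean. These values are invented to show the logic and say nothing about the likely data. Week-by-week reporting would separate the three.

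**3. What a within-child change could deliver**

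Input: n = 12 (Sample section), assuming all 12 children contribute both periods and changes are roughly normal.

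Half-width of the 95% interval = t(0.975, 11)/√12 × SD of change = 2.201/3.464 × SD = 0.635 × SD.

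The documents give no SD, so a range is assumed:

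- SD 40 mg/dl: 0.635 × 40 ≈ 25
- SD 60 mg/dl: 0.635 × 60 ≈ 38
- SD 80 mg/dl: 0.635 × 80 ≈ 51

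At an SD of 60, an observed mean change of 30 mg/dl would carry an interval from 30 − 38 = −8 to 30 + 38 = 68, which includes zero. The estimate is interpretable but imprecise, and more so if fewer than 12 children have both periods.

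**The case against.** The best defence is that this is a feasibility study seeking only preliminary evidence. Description is an appropriate level of analysis, readings are gathered at every session, and a sensible analyst would show them by week. Readings stored in the meter before session 1 would predate the programme, so a baseline may be within reach already. No decision rule, sample size or safety action hangs on Aim 2.b.

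Most of this stands, and it limits how far the point can be taken. A reader might infer three stronger things that the documents do not support:

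- *That no effect or change can be estimated at all.* The shortfall is in the stated analysis, not the data. Weekly collection, meter memory and the assessment one week after the programme would allow a within-child change if the plan asked for one.
- *That the plan pools all weeks and so dilutes any effect.* If an effect grew linearly from zero in week 1, a pooled mean would hold (0 + 0.2 + 0.4 + 0.6 + 0.8 + 1.0)/6 = 0.5 of the final effect. But pooling is nowhere stated, and describing the data by week fits the text at least as well.
- *That adding a before/after contrast would yield a programme effect.* Without a control group it would not. Children enter because they are newly diagnosed or because their latest HbA1c is 8.0 or more, so regression to the mean and early post-diagnosis change could each produce a shift.

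What the defence does not remove is that collecting data weekly is not the same as comparing weeks. The plan commits to no by-week display, no baseline and no contrast for this outcome, although it states a contrast for three of its other analyses.

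**Conclusion.** The point holds in a limited form. Aim 2.b is worded as a question about effect, but the stated analysis describes the bedtime-to-fasting-morning difference and specifies no comparison over time. Followed as written, it reports a level and leaves open whether control improved, held or worsened.

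This rests on the text of the aims alone. The pooling illustration applies only if weeks are pooled. The precision figures rest on 12 complete children and assumed SDs of 40 to 80 mg/dl.

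It should be fixed, but it need not hold up the study: it affects one of four preliminary indicators, the main purpose is feasibility and acceptability, and the remedy uses readings that are already collected or stored. It is best settled before session 1, because earlier stored readings not secured then may be unavailable later.

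**What to change.** Restate the Aim 2.b analysis as a within-child change:

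1. For each child, compute the mean signed and the mean absolute bedtime-to-morning difference in an early period and in the last programme week or weeks. The early period is the stored meter readings from before session 1 where available, and otherwise week 1, labelled as such.
2. Report the mean of the per-child changes with a 95% confidence interval, together with the weekly means.
3. State in advance the length of the late period and how stored pre-session readings are classed as bedtime or fasting, for example by clock-time windows. No family record is described for that period to identify them.
4. Describe the result as uncontrolled change over time, open to regression to the mean and early post-diagnosis change, and not as an effect of the programme.

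The cost is a few sentences of plan text, a classification rule, and a meter download at session 1 that reaches back before the programme. Some children, especially the newly diagnosed, will have few earlier readings. A week-1 baseline is weaker because the programme has already begun, so the report should show how many children contribute each type of baseline. The estimate will remain imprecise at this sample size.
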